#### **10.4.2. Fistula Abandonment**

The index AV fistula will be classified as abandoned if any of the following conditions are met:

- For subjects undergoing hemodialysis during the course of study participation:
  - The fistula was never used for 2-needle dialysis during the study period (fistula will be considered abandoned on the day of creation);
  - The fistula can no longer be used for 2-needle dialysis and there is no expectation of future use
  - Placement of a new vascular access for hemodialysis

- The fistula undergoes surgical revision of the anastomosis.
- For subjects who were not on hemodialysis on day of enrollment and who never initiated hemodialysis during the course of study participation:
  - The fistula was designated as being abandoned by the investigator. The investigator's decision to abandon the fistula may be based on:
    - The results of a clinical evaluation of the fistula
    - In some instances, at the discretion of the investigator, the decision to abandon the fistula may be based on the results of an imaging study (ultrasound or angiogram)
  - The fistula undergoes surgical revision of the anastomosis
  - Placement of a new vascular access for hemodialysis.

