## 7. INVESTIGATIONAL PLAN

### 7.1. Overall Study Design

This is a Phase 3, multicenter, randomized, single blind, controlled, adaptive study designed to evaluate the efficacy and safety of the use of the Sirolimus-eluting Collagen Implant (SeCI) in subjects who are on hemodialysis or are preparing for hemodialysis and are undergoing surgical creation of an AV fistula in comparison to subjects who do not receive the implant.

Subjects of either gender, who are at least 18 years of age, undergoing hemodialysis or are expected to initiate hemodialysis within 6 months of study enrollment, and require a new single-stage radiocephalic or brachiocephalic end-to-side fistula will be eligible to participate in this study. It is expected that all subjects will be enrolled across approximately 20 sites and each enrolled subject will be followed for one year from the time of fistula creation.

Subjects who meet eligibility criteria and undergo successful AV fistula creation will be eligible for enrollment. The study plans to enroll approximately 240 subjects. Of these, the first subject enrolled by a participating surgeon will be a run-in subject; run-in subjects will not be part of the randomized set; all run-in subjects will receive the SeCI. The intent of enrolling run-in subjects in the clinical study is to familiarize the investigators with the implant procedure. Approximately 220 subjects will be randomized in a 1:1 ratio using permuted block randomization stratified by surgeon and fistula location (radiocephalic or brachiocephalic) to yield approximately 200 evaluable subjects. The randomized cohort will include a minimum of 100 evaluable subjects who are on hemodialysis at the time of the index procedure.

Subjects who are on hemodialysis at the time of enrollment will undergo evaluations to determine fistula suitability for cannulation starting no earlier than day 28 post index procedure; the frequency of assessments for cannulation suitability will be at the discretion of the investigator and/or designee. The decision to proceed with first cannulation will be made by the investigator based on clinical assessment of the fistula. In addition, subjects who have not initiated hemodialysis by:

- Day 90 post index procedure, and the index fistula has not been abandoned, a vascular ultrasound will be performed at the 3 month follow up visit,

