### **8.3. Withdrawal or Discontinuation**

Following randomization, neither the sponsor nor the investigator should discontinue any subject from the study. However, subjects may be discontinued from the clinical study for any of the following reasons:

- Withdrawal of consent by the subject; or
- Lost to follow-up

Although each subject is expected to remain in this study for the duration of follow-up, all subjects have the right to withdraw at any point during the study without prejudice. Withdrawal of consent for follow-up should be accompanied by documentation of the reason for withdrawal. Withdrawal of consent for follow-up visits should be distinguished from withdrawal of consent for non-patient contact follow-up, e.g., medical records checks. Preferably the subject should withdraw consent in writing and, if the subject or the subject's representative refuses or is physically unavailable, the site should document and sign the reason for the subject's failure to withdraw consent in writing. The investigator and/or designee will, if at all possible, complete all End of Study evaluations on subjects who withdraw from the study. If a subject chooses to withdraw from the study because of an adverse event, the subject should be explicitly asked about the contribution of possible adverse events to their decision to withdraw consent; any adverse event information elicited along with the principal specific event and any related test results must be captured in the source document and eCRF. Subjects who discontinue participation in the study due to an adverse event experienced during study conduct will, at minimum, be followed until resolution or until stabilization.

[figure not shown]
If a subject is lost to follow-up, the investigator and/or designee will make at least 3 phone attempts to reach the subject. If the phone attempts are unsuccessful, the site will mail a certified letter to the subject's last known address requesting they return for evaluation. If a subject dies during the course of the study, they will not be considered withdrawn from the study, but rather no further follow-up will be required. The reason for withdrawal or discontinuation will be documented in the subject's source document and eCRF.

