### **10.2.3. Secondary Patency**

Secondary patency, defined as the interval from the time of access placement until access abandonment.

Secondary patency will be evaluated based on

- Clinical evaluation of the fistula,
- Subject's dialysis session records (for subjects who are undergoing hemodialysis),
- Imaging results (Duplex ultrasound and/or angiogram - if applicable and available), and,
- Access event data.

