#### **10.4.3. Censored Events**

Subjects experiencing censoring events before an endpoint is observed will be included in the statistical analysis up to the time at which they achieve the censoring event. They will be censored (excluded) from the analysis after that time point. These censoring rules apply to all efficacy endpoints.

Censored events include:

- Death
- Renal transplantation
- Transfer to peritoneal dialysis

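### The day-0 abandonment rule gives 0 days of secondary patency to a patent fistula in a subject who starts hemodialysis late by catheter, and it has no stated order against the censoring rules

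*Combined protocol and SAP*

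**What the plan says.** Section 10.2.3 defines the endpoint: "Secondary patency, defined as the interval from the time of access placement until access abandonment". The date of abandonment therefore fixes the result.

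Section 10.4.2 has two branches. For subjects on hemodialysis at any time during participation, one criterion is "The fistula was never used for 2-needle dialysis during the study period (fistula will be considered abandoned on the day of creation"). It sets no minimum follow-up, no minimum time on dialysis and no condition on patency. For subjects who never start hemodialysis, abandonment needs the investigator's designation, surgical revision of the anastomosis or a new access, and nothing is back-dated. Both branches list "Placement of a new vascular access for hemodialysis" without saying whether a catheter counts. The visit checklists in 7.3 do name a catheter as a new access.

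Section 10.4.3 begins its list with "Censored events include" and gives death, renal transplantation and transfer to peritoneal dialysis. It adds: "These censoring rules apply to all efficacy endpoints". Section 8.3 gives two reasons for discontinuation, "Withdrawal of consent by the subject" and "Lost to follow-up"; neither is in the 10.4.3 list. Sections 10.4.2 and 10.4.3 do not refer to each other.

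**The concern.** The day-0 rule suits a subject who dialyzes throughout and whose fistula never works. It fits poorly for someone enrolled before dialysis, as inclusion criterion 3 allows, who starts by catheter near the end of follow-up. That fistula may have been patent for most of a year, with little opportunity for use. Starting dialysis moves the subject from one branch of 10.4.2 to the other and removes all the observed patency. Another endpoint in the same trial may count the fistula as a success.

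The second gap is precedence. For a dialysis subject who dies or is transplanted before first cannulation, 10.4.2 and 10.4.3 give different answers.

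Secondary patency is third of the four listed secondary endpoints. Testing is step-down (13.3.4), so if the listed order is used its test counts only after two earlier successes. Its estimate will be reported either way. Abandonment also counts as one intervention in 10.2.4, so the re-intervention rate may be touched.

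**Working it through.** **The plan's own figure.** Section 13.2 gives about 82% power for FSD6 at 45% vs 65% with N=200. A two-proportion calculation with 100 per arm gives 81.6%, which agrees. FSD6 does not use the abandonment rule, so this figure is unaffected. No rate or power is stated for secondary patency; the patency figures below are assumptions.

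**One subject followed through the text.** Not on hemodialysis at enrollment; starts by catheter on day 340; fistula patent and meeting both ultrasound thresholds at 6 and 12 months; no 2-needle session by day 360.

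| Rule | Result |
|---|---|
| FSD6, 10.1 part b (no dialysis by day 150) | success |
| FSD12, 10.2.1 part b (no dialysis by day 330) | success |
| Secondary patency, never-used criterion | event, 0 days |
| Secondary patency, if a catheter is a new access dated at placement | event, 340 days |
| Secondary patency, if neither criterion applied | censored, 360 days |
| Secondary patency, had the subject never dialyzed | censored, 360 days |

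**Precedence.** Under 7.1, subjects on hemodialysis at enrollment have "evaluations to determine fistula suitability for cannulation starting no earlier than day 28 post index procedure". One who dies on day 20 will ordinarily have had no 2-needle use. Section 10.4.2 gives an event at day 0; 10.4.3 gives censoring at day 20. Section 10.4.3 applies when the censoring event comes before the endpoint, but a back-dated endpoint always comes first.

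**How many late starters.** Assume exponential time to dialysis start with a median of 180 days, suggested by inclusion criterion 3. The share not yet started by day t is 0.5^(t/180).
- Start between days 330 and 360: 0.281 - 0.250 = 3.1%.
- Start between days 300 and 360: 0.315 - 0.250 = 6.5%.
- Multiply by an assumed 20% to 80% starting by catheter. The upper value is the background figure in 5.4 for all US patients; it is probably lower with a fistula in place. Result: 0.6% (3.1% x 0.2) to 5.2% (6.5% x 0.8).
- Medians of 4 or 9 months give 0.5% to 5.3%.

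This counts only starts in the last 30 to 60 days and assumes no 2-needle use before exit.

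**Effect on the test.** Assumed 12-month patency 64% vs 80%, 110 per arm (220 randomized 1:1), 55 predialysis per arm, exponential abandonment, follow-up to day 360, unstratified log-rank at two-sided 0.05. A share q of predialysis subjects with a patent fistula is moved to day 0. Expected 12-month patency is S x (1 - q/2), because half of each arm is predialysis.

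| q, control / treatment | Patency | Difference | Power |
|---|---|---|---|
| 0 / 0 | 64.0% vs 80.0% | 16.0 points | about 76% |
| 1% / 1% | 63.7% vs 79.6% | 15.9 | about 75% |
| 2.5% / 2.5% | 63.2% vs 79.0% | 15.8 | about 74% |
| 5% / 5% | 62.4% vs 78.0% | 15.6 | about 71% |
| 10% / 5% | 60.8% vs 78.0% | 17.2 | about 79% to 80% |

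At q = 5% about 1.8 control and 2.2 treatment subjects are back-dated (55 x 0.64 x 0.05 and 55 x 0.80 x 0.05). The difference widens whenever 0.64 x q(control) exceeds 0.80 x q(treatment), that is, when the control share is more than 1.25 times the treatment share.

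**The case against.** The day-0 rule is objective and looks deliberate: a fistula that a dialysis subject never uses has failed. Section 7.1 requires at least 100 evaluable subjects on hemodialysis at the index procedure, and for them the rule is defensible. Removing it for everyone would censor as still patent a subject who dialyzes by catheter all year with a never-used fistula and no recorded decision. That objection stands, and it confines the fix to subjects who start hemodialysis after enrollment. The effect is also small, and the SAP that 13.1 describes may already settle the dating; it is not in the text reviewed.

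Three stronger readings are tempting but not supported.
- **Bias toward no difference.** This follows only if both arms have similar shares. Patent but uncannulated fistulas may be commoner in control, and then the difference can widen.
- **Withdrawals and early losses all score day 0.** Use after loss is unobserved, a log-rank test ordinarily censors at last contact, and the 10.4.3 list may not be exhaustive. Section 10.2.4 also censors incomplete follow-up for the re-intervention rate, though only after abandonment. The text should confirm censoring, but it does not dictate day 0.
- **Any bridging catheter ends secondary patency.** The checklist item records events; it does not define abandonment, and 10.2.2 allows catheter use alongside a maturing fistula. The term is undefined, and the documents give no basis for a count.

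**Conclusion.** The point holds for late starters and for precedence. Applied as written, 10.4.2 gives 0 days of secondary patency to a fistula that 10.1 or 10.2.1 can count as a success, and it conflicts with 10.4.3 for a dialysis subject who dies or is transplanted before first cannulation. Only secondary patency, and possibly the re-intervention rate, is affected.

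Under the stated assumptions, equal back-dating of 1% to 5% costs about 1 to 5 points of power, with roughly two subjects per arm at the upper end. The patency rates, the predialysis split, the dialysis-start distribution and the catheter shares are assumptions, and the planned stratification was not modeled. The contradiction itself needs none of them. It should be fixed because the change is cheap and is best made before outcomes are known.

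**What to change.** For the endpoint definition only, with no change to clinical management:

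1. State that 10.4.3 censoring takes precedence over the day-0 rule. Confirm that withdrawal of consent and loss to follow-up are censored at last contact.
2. Keep day-0 dating for subjects on hemodialysis at enrollment. For subjects who start later, do not date abandonment before the start of hemodialysis unless an abandonment event is documented earlier. If hemodialysis starts after day 330, the protocol's own FSD12 cut-off, and no abandonment event is documented, censor at end of follow-up. Report the current day-0 definition as a sensitivity analysis.
3. Reconcile the new-access criterion in 10.4.2 with the checklists that name a catheter. Settle this together with item 2: if a catheter counts, its placement is itself a documented event, and the late catheter starter is not censored.

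The cost is protocol and SAP wording and one added analysis. Access events, new accesses and reasons for discontinuation are already collected, so no visits are added. The downside is a date slightly less simple to derive than a uniform day 0.

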#### **10.4.3. Censored Events**

Subjects experiencing censoring events before an endpoint is observed will be included in the statistical analysis up to the time at which they achieve the censoring event. They will be censored (excluded) from the analysis after that time point. These censoring rules apply to all efficacy endpoints.

Censored events include:

- Death
- Renal transplantation
- Transfer to peritoneal dialysis

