g Access assessment to document fistula patency and fistula development status. Evaluations include thrill and bruit assessment, arm elevation test, and augmentation test. Access assessments should be performed by delegated dialysis unit personnel.

h Clinical exam to document wound healing, any local problems such as infection, wound dehiscence, unexpected amount of arm swelling, etc., and evaluation for presence of steal syndrome (e.g. pain in digits, discoloration, cold fingers, blue fingers, etc.).

i For subjects on hemodialysis at the time of enrollment or subjects who initiate dialysis within 28 days of index procedure, cannulation assessment will start no earlier than 28 days post index procedure with subsequent assessments occurring at discretion of the investigator and/or designee. The decision to proceed with first cannulation will be based on the investigator's clinical assessment.

j For subjects who do not initiate hemodialysis by Day 90 and the index fistula has not been abandoned, a duplex ultrasound must be performed at the 3 month follow up visit.

k For subjects whose index fistula is not in use for hemodialysis on day 150 and the index fistula has not been abandoned, a duplex ultrasound must be performed at the 6 month follow up visit.

l For subjects whose index fistula is not in use for hemodialysis on day 330 and the index fistula has not been abandoned, a duplex ultrasound must be performed at the 12 month follow up visit.

m Record adverse events and concomitant medications that are associated with or occurred during an SAE or vascular access events. See sections 9.7 and 12.

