# 10. ASSESSMENT OF EFFICACY

## 10.1. Primary Endpoint

The primary endpoint of the study is Fistula Suitability for Dialysis at 6 months (FSD6) defined as a composite of:

- a. For subjects who are on hemodialysis by day 150, suitability for dialysis will be determined by the ability to use the fistula for dialysis using 2-needles with a mean dialysis machine blood pump speed of  $\geq 300$  mL/min for at least two-thirds of the dialysis sessions performed during a 30 day suitability ascertainment period that will commence on day 150.
- b. For subjects who are not on hemodialysis on day of enrollment and who do not initiate hemodialysis by day 150, suitability for dialysis will be determined by a vascular ultrasound performed at the 6 month follow up visit. Suitability for dialysis

will be defined as a fistula with an access vein diameter (AVD) of  $\geq 6$  mm (internal diameter) and an access blood flow of  $\geq 500$  mL/min.

Evaluation of Fistula Suitability for Dialysis at 6 months:

- For subjects undergoing hemodialysis during the suitability ascertainment period, suitability for dialysis will be based on the subject's dialysis session records
- For subjects who are not on hemodialysis on the day of enrollment (i.e. on the day of fistula creation) and who do not initiate hemodialysis by day 150, suitability for dialysis will be based on duplex ultrasound results performed at the 6 month follow up visit.

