### **10.2.2. Fistula Maturation by Day 90**

Fistula Maturation by Day 90, defined as a composite of:

- a. For subjects who are on hemodialysis by day 90:
  - Three consecutive dialysis sessions using 2-needles with a mean dialysis machine blood pump speed of  $\geq 300$  mL/min, the first of these three dialysis sessions completed on or before 90 days from the time of creation of the AV fistula, or
  - Two-needle dialysis on or before 90 days with no further use of the catheter prior to achieving three consecutive dialysis sessions using 2-needles with a mean dialysis machine blood pump speed of  $\geq 300$  mL/min.
- b. For subjects who do not initiate hemodialysis by day 90, fistula access vein diameter (AVD) of  $\geq 6$  mm (internal diameter) and an access blood flow of  $\geq 500$  mL/min determined by a vascular ultrasound performed at the 3-month follow up visit.

Evaluation of Fistula Maturation is based on subject's dialysis session records

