#### **13.3.3. Main Analysis**

The null hypothesis for FSD6 is that the population proportions of subjects with FSD6 for the treatment group receiving the sirolimus eluting collagen implant [ $p_I$ , where “I” indicates implant treatment] and the control group ( $p_C$ , where “C” indicates control group) that does not receive the implant are equal. The alternative is that the proportion of subjects with FSD6 is not equal for the treatment group and the control group.

Algebraically, these hypotheses are stated as follows, where “H0” indicates the null hypothesis and “Ha” indicates the alternative hypothesis:

$$H0: p_I = p_C$$

$$Ha: p_I \neq p_C$$

“I” indicates implant treatment, and “C” indicates control treatment.

For the primary endpoint of FSD6, the proportions will be compared between treatment and control using a logistic regression model with factors for treatment and stratum.

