### **13.3.4. Secondary Efficacy Endpoints**

Time to event secondary endpoints will be analyzed by stratified log-rank test. Binary endpoints will be compared between treatments via the same logistic regression model as for the primary efficacy endpoints. Continuous secondary endpoints will be compared via analysis of covariance for a model including factors for treatment, strata, and baseline covariate if available, or non-parametric rank tests if normality or homogeneity assumptions appear substantially violated. Overall study-wise type 1 error control across secondary endpoints will be addressed via step-down testing. That is, the secondary endpoints will be tested one at a time in step-down order, until the first non-significant result, after which step-down testing will stop for purposes of supporting conclusions.

Individual patient listings will be provided for the primary and secondary endpoints.

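### Section 10.4.3 extends a time-to-event censoring rule to the binary FSD6, FSD12 and Day 90 endpoints, where its natural reading drops randomized subjects from the analysis

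*Combined protocol and SAP*

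**What the plan says.** Section 10.4.3 keeps a subject in the analysis until death, renal transplantation or transfer to peritoneal dialysis, if that comes before the endpoint is observed. It then continues: "They will be censored (excluded) from the analysis after that time point. These censoring rules apply to all efficacy endpoints". No endpoint is exempted.

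Three of the endpoints covered are yes/no outcomes read at a set time:

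- **FSD6 (10.1).** For subjects on hemodialysis, the fistula must support two-needle dialysis at the required pump speed "for at least two-thirds of the dialysis sessions performed during a 30 day suitability ascertainment period that will commence on day 150". For those not yet on hemodialysis it is read from the 6-month ultrasound.
- **FSD12 (10.2.1).** The same construction, starting on day 330.
- **Day 90 maturation (10.2.2).** Part (a) can be met by three consecutive qualifying sessions, "the first of these three dialysis sessions completed on or before 90 days from the time of creation of the AV fistula". Part (b) uses the 3-month ultrasound.

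For FSD6, section 13.3.3 says "the proportions will be compared between treatment and control using a logistic regression model with factors for treatment and stratum". Section 13.3.4 adds: "Binary endpoints will be compared between treatments via the same logistic regression model as for the primary efficacy endpoints".

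Section 13.3.1.1 puts every randomized subject in the full analysis set. The synopsis adds only that they received access surgery. Section 8.3 says a subject who dies is not a withdrawal, and lists only withdrawn consent and loss to follow-up as reasons for discontinuation. Sections 13.1 and 13.3.1 leave derivations and analysis-set details to the SAP, but no separate SAP text appears in the combined document.

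**The concern.** Censoring has a meaning when the analysis has a time axis: the subject contributes time at risk up to the event. A logistic model of a single outcome has no such axis. With the protocol glossing censored as excluded, a subject with a listed event before ascertainment most naturally has no row in the model.

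Take a hemodialysis subject whose fistula is lost for good on day 60 and who is transplanted on day 100. There are no sessions in the window that opens on day 150, so on this reading the subject disappears from the primary analysis. The same subject, still on hemodialysis, would count as a failure. Whether a known failure counts then depends on an event after randomization. If such exclusions differ between arms, the comparison can be biased in either direction. Two analysts could also build different FSD6 data sets from the same text.

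**Working it through.** **1. The plan's own figure.** Sections 13.2 and 7.1 give 45% vs 65%, two-sided alpha 0.05, 100 analysed per arm, and 220 randomized to yield about 200 evaluable. With the pooled-variance normal approximation:

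power = Φ{[d√n − 1.96√(2p̄q̄)] / √(p₁q₁ + p₂q₂)} = Φ{[0.20×10 − 1.96×√0.495] / √0.475} = Φ(0.90) = 81.6%.

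The stated value is about 82%, so it is correct. The allowance is 220 − 200 = 20 non-evaluable subjects (20/220 = 9.1%). The reasons for non-evaluability are not stated.

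**2. Day 90 maturation.** Under part (a), success can be seen before a listed event (for example, three good sessions by day 60). Failure is not established until day 90 has passed. A rule that acts only on unobserved endpoints therefore keeps early successes and removes subjects who have not yet succeeded. Under part (b), success and failure both come from the same ultrasound, so there is no such asymmetry.

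**3. Type I error.** The documents give no event rates and no arm imbalance, so these are assumptions: 110 per arm, a true rate of 45% in both arms, and 5, 10 or 20 subjects excluded in total on average. The test is a pooled two-proportion z test, standing in for the stratified logistic model, with 1,000,000 simulated trials per setting. With no exclusion the error is 4.94%.

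| Split control/treatment; share of excluded who would have failed | 5 | 10 | 20 |
|---|---|---|---|
| 50/50; all | 5.18% | 5.02% | 5.05% |
| 40/60; all | 5.14% | 5.23% | 5.99% |
| 30/70; all | 5.32% | 5.84% | 8.72% |
| 30/70; 75% | 5.16% | 5.21% | 5.79% |
| 30/70; 55% (same as everyone) | 5.10% | 5.04% | 5.08% |

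Differences of 0.1 to 0.2 points reflect the discreteness of the test.

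Hand check of the largest value: each arm expects 0.45×110 = 49.5 successes. Losing 6 and 14 failures gives 49.5/104 = 47.6% and 49.5/96 = 51.6%, a spurious 4.0 points. The standard error is √[0.495×0.505×(1/104 + 1/96)] = 0.0708, so the shift is 0.56 standard errors. The error is P(Z > 1.40) + P(Z < −2.52) = 8.1% + 0.6% = 8.7%.

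**4. Reported rates and odds ratio.** Losing failures equally under no effect lifts the observed rate from 45% to 49.5/107.5 = 46.0%, 49.5/105 = 47.1% or 49.5/100 = 49.5%. The odds ratio behaves differently. If a fraction f of failures is lost in each arm at 45% vs 65%, it is [0.65/(0.35(1−f))] / [0.45/(0.55(1−f))] = 2.27 for any f. Equal fractions are not equal counts, however. Losing 10 failures per arm of 110 gives (71.5/28.5)/(49.5/50.5) = 2.56.

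**5. Sensitivity at the significance threshold.** Section 13.2 gives 45% vs 59% as the smallest significant observed difference, and 45/100 vs 59/100 gives p = 0.048. If 10 more subjects per arm count as failures, 45/110 vs 59/110 gives p = 0.059. With unequal loss, 47/105 vs 56/95 (p = 0.045) becomes 47/110 vs 56/110 (p = 0.22), while 43/95 vs 63/105 (p = 0.037) becomes 43/110 vs 63/110 (p = 0.007). These counts are illustrative.

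**6. Power if listed events count as non-success.** With 110 per arm and both rates multiplied by (1 − r), power is 82.7% at r = 3%, 81.0% at 5% and 77.3% at 9.1%.

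**The case against.** A reader might infer that the rule can only mean dropping subjects. The text does not go that far. It acts only before an endpoint is observed, so a fistula already lost for good, or an event late in the day 150 to 180 window, could be treated as observed. An unseen SAP could say so. This stands: removal is the natural reading, not the only one.

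A reader might also infer that usable data are thrown away. Table 7 requires a 6-month ultrasound "For subjects whose index fistula is not in use for hemodialysis on day 150 and the index fistula has not been abandoned", and that could include a transplanted subject who never started hemodialysis. But section 10.2.4, on re-intervention rate, ends fistula evaluation at a censored event. Section 5.3 notes that sirolimus is marketed to prevent kidney-transplant rejection. A transplanted control could thus receive the study drug systemically before the scan, so stopping evaluation at transplant is defensible.

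Loss was planned for, with 200 evaluable of 220. That shows losses were expected but does not say how these subjects are scored.

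Finally, 8.7% needs every non-evaluable place to be a listed event in a failed fistula, split 30/70 with no true effect. The implant would have to change transplant, death or modality transfer without changing suitability, and subjects and nephrologists are blinded (9.2.3). This also stands: 8.7% is a bound, not an expectation.

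**Conclusion.** The concern holds as a fault in the wording of 10.4.3 that reaches the primary endpoint. As written, the natural effect is an exclusion after randomization that can depend on fistula outcome, at odds with the full analysis set. It should be corrected before unblinding.

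The size is probably modest. With balanced loss alpha holds. If equal fractions of failures are lost, success rates rise but the odds ratio does not change. Appreciable bias needs unequal loss concentrated in failures. All of this rests on assumed event counts and splits, because the documents give none. The sample size calculation is not at fault. The documents do not support a claim that the trial's error rate is materially inflated, or that Day 90 maturation is one-sided beyond part (a).

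**What to change.** 1. In 10.4.3, limit censoring to secondary patency, primary patency, TTFD and re-intervention rate.
2. For FSD6, FSD12 and Day 90 maturation, keep all randomized subjects in the analysis. Score as failure a subject whose fistula was documented, on a date before the event, as abandoned or permanently unusable; 10.4.2 already has suitable wording: "The fistula can no longer be used for 2-needle dialysis and there is no expectation of future use". Do not use its clause for never-used fistulas, "fistula will be considered abandoned on the day of creation". Cannulation assessment starts no earlier than day 28, so a hemodialysis subject transplanted on day 20 would become a failure before the fistula could be tested. Keep as success a subject who had already met Day 90 maturation.
3. For the remaining subjects with a listed event, fix one rule before unblinding, identical in both arms, for example non-success. Without it, step 2 would count early FSD6 failures while fistulas working well at the event were dropped. Add a tipping-point sensitivity analysis that includes the exclusion approach. Do not score from an ultrasound done after transplant, because immunosuppression could confound it.
4. If non-success is chosen, restate power over a range of event rates: about 83%, 81% and 77% at 3%, 5% and 9%, for 220 randomized and 45% vs 65% among the others.

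The cost is protocol and SAP wording, a recorded date and criterion for permanent failure (secondary patency already needs an abandonment date), one extra analysis, and possibly slightly lower stated power.
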